#### The secondary objective are to

(a) To quantify salivary levels of pyruvic acid, citric acid, 2-ketoglutamic acid, succinic acid, malic acid and fumaric acid at baseline, and at 6 months follow up, and determine if changes in these levels contribute towards the effect of intervention versus control on the caries outcome at 2 years.

(b) To determine if salivary acid levels correspond with microbiome eubiosis or dysbiosis by studying the oral bacterial microbiome and fungal mycobiome in a subset of 60 children at baseline, and at 6 months follow up.

# 12 SAFETY REPORTING

Safety reporting in clinical trials is a legal and ethical requirement and it is imperative that all applicable requirements detailed here are followed during the trial.

## 12.1 **Terms and Definitions**

## 12.1.1 Adverse Event (AE)

Any untoward medical occurrence, unintended disease or injury or any untoward clinical signs (including an abnormal laboratory finding) in subjects, users or other persons whether or not related to the intervention under investigation.

### 12.1.2 Related Adverse Event (Related AE)

An AE which resulted from administration of any of the research procedures – i.e. assessed as "probably", "possibly" or "almost certainly" related to the trial procedures.

### 12.1.3 Related Unexpected Adverse Event (RUAE)

A Related AE which is not expected, i.e. not consistent with the known effects of the trial procedures.

### 12.1.4 Serious Adverse Event (SAE)

An adverse event which meets the definition of "serious".

### 12.1.5 Related Serious Adverse Event (Related SAE)

A SAE which is assessed to be "probably", "possibly" or "almost certainly" related to the trial procedures.

### 12.1.6 Related Unexpected Serious Adverse Event (RUSAE)

A Related SAE which is not expected, i.e. not consistent with the known effects of the trial procedures.

## 12.2 Assessment of Seriousness

The assessment of seriousness of safety events should be performed by an appropriately delegated, qualified CHOICE member of the site research team.

A #safety event (whether or not assessed as related to the trial) is assessed as serious if it:

- Results in death;
- Is life-threatening (i.e. the investigator considers the event places the subject at immediate risk of death from the experience as it occurred (this does not include an adverse experience that, had it occurred in a more severe form, might have cause death);
- Requires hospitalisation or prolongation of existing hospitalisation (hospitalisation is defined as an inpatient admission, regardless of length of stay, even if the hospitalisation is a precautionary measure for continued observation);

- Results in persistent or significant disability or incapacity (substantial disruption of one's ability to conduct normal life functions);
- Consists of a congenital anomaly or birth defect (in offspring of trial participants, or their partners, regardless of time of diagnosis), or
- Is otherwise considered medically significant by the investigator.

*\*safety event / reaction applies apply to either AEs, or ARs, or Related AEs, or Adverse Device Effects* 

## 12.3 Severity of Adverse Events

All adverse events should be assessed for severity. The assignment of the severity/grading should be made by a suitably qualified and delegated Dentist (Investigator) responsible for the care of the participant using the definitions in the table below:

### 12.3.1 Table 1: Severity Grading

Severity	Description
Mild	Does not interfere with routine activities.
Moderate	Interferes with routine activities.
Severe	Impossible to perform routine activities.
Life-Threatening	Causes immediate threat to life.
Death	Event results in death.

N.B. A distinction is drawn between **serious** and **severe** AEs. Severity is a measure of intensity (see above) whereas seriousness is defined using the criteria in Section 12.2. Hence, a severe safety event need not necessarily be a "serious" safety event.

## 12.4 Assessment of "Causality" - Relationship to Trial Treatment/Intervention

The assessment of relationship of adverse events to the intervention is a clinical decision based on all the available information at the time of the event. The assignment of the causality should be made by a suitably qualified and delegated Dentist (Investigator) responsible for the care of the participant using the definitions in the table below:

Description			
There is no evidence of any causal relationship.			
N.B. An alternative cause for the AE should be given			
There is little evidence to suggest there is a causal relationship (e.g. the event did not			
occur within a reasonable time after administration of the trial intervention). There is			
another reasonable explanation for the event (e.g. the participant's clinical condition,			
other concomitant treatment).			
There is some evidence to suggest a causal relationship (e.g. because the event occurs			
within a reasonable time after administration of the trial intervention). However, the			
influence of other factors may have contributed to the event (e.g. the participant's			
clinical condition, other concomitant treatments).			
There is evidence to suggest a causal relationship and the influence of other factors is			
unlikely.			

### Table 2: Definitions of Causality

Almost certainly	There is clear evidence to suggest a causal relationship and other possible contribution			
	factors can be ruled out.			

In the case of discrepant views on causality between the dentist and others, the opinion of the dentist will never be downgraded and the REC will be informed of both points of view.

For the CHOICE trial, only events that are classed as serious and possibly, probably or almost certainly related will be reported by participating site.

## 12.5 Assessment of "Expectedness"

It is not a regulatory requirement for a reporting dentist to provide their opinion of expectedness. Therefore, the reporting physician at the trial sites will not be asked to make the assessment of expectedness. The assessment of expectedness will be made by the Chief Investigator.

An event will be considered **unexpected** if it is not listed within the current and approved protocol (see Table 2: Expected Events) for the study at the time of the event's onset. This includes events that are more frequently reported or more severe than previously reported.

A serious adverse event whose causal relationship to the intervention is assessed by the dentist/delegated other as "possibly", "probably", or "almost certainly" is considered to be a related SAE. If this is then classified by the CI or delegated other as unexpected then this event should be reported as a RUSAE.

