# 7.1 Blinding

Where possible, final dental assessments at 24 months (+/- 3) will be undertaken by a single, trained examiner who will be blind to child's group allocation. If a single examiner is not feasible, for example due to rapid recruitment, then a reserve plan will be used that will include a team of trained assessors, to undertake the final dental assessments. The examiner/s will be independent to the general dental practices and will not have access to documentation containing trial allocation.

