### 10.8.6 Safety Assessments

Active monitoring of safety events experienced by trial participants will take place from randomisation until 24 months (+/- 3 months) post randomisation. Reportable safety events will include:

• A serious adverse event related to the trial procedures or intervention

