### 12.9.1 Related Serious Adverse Events

Related SAEs should be reported to the LCTC within 24 hours of the local site becoming aware of the event using the SAE eCRF form. The SAE form asks for the nature of the event, date of onset, severity, corrective therapies given, outcome and causality. The reporting dentist should assign the causality of the event. Additional information should be provided within 5 days if the event has not resolved at the time of reporting. As a minimum, the SAE form should contain the following information:

Minimum information required from site	Corresponding data/information
Valid registration number and Sponsor study number	ISRCTN number and sponsor study number
One identifiable coded subject	Patient study number
One identifiable reported	Study site number
	Reporting site research team member (PI/delegate)
One related serious safety event	Description of the event, including date of onset
	The reason why the event is classed as serious
One suspect intervention	The CHOICE intervention
A causality assessment	Investigator assessment of causality

Once reported to the LCTC, the CI (or delegated other) will be asked to review the event and provide their opinion on expectedness. Any Related and Unexpected Serious Adverse Events (RUSAEs) must be emailed to the REC by LCTC using the HRA non-CTIMP safety report to REC form. These must be sent within 15 days of LCTC becoming aware of the event. All dentists will be informed of all RUSAEs occurring throughout the trial. Local dentists should report any RUSAEs as required locally.

When reporting related SAEs, the reporting dentist should apply the following criteria to provide information relating to event outcomes: resolved; resolved with sequelae (specifying with additional narrative); not resolved/ongoing; ongoing at final follow-up; fatal or unknown.

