# 12.10 Flowchart for Site Reporting Requirements of Adverse Events

## 12.11 Investigator Reporting Responsibilities

The PI is responsible for ensuring that all safety events requiring recording on this study which the local research team becomes aware of are reported to LCTC. It is the responsibility of the PI/Co-PI as recorded on the Delegation Log (medically qualified person) to assess the seriousness and causality of events. When documenting any adverse events the correct medical terminology must be used.

Safety events which meet the definition of "serious" and related (possibly, probably or almost certainly) must be reported in more detail to the LCTC on the SAE eCRF form and must be reported **immediately and in no circumstances later than 24 hours from becoming aware** where they will be appropriately processed.

The SAE eCRF form should be completed by an appropriately delegated member of the research team; the assessments of seriousness and causality must be performed by an appropriately medically qualified and delegated person/dentist. Minimum reporting information must be provided in initial reports for all studies (see section 12.9.1).

Safety events should be reported by the site in accordance with local policy.

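### The protocol gives two conflicting tests for a related SAE, so serious events from trial procedures may be missed or classified differently between sites, notably in controls

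*Protocol*

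**What the plan says.** Three places in the Protocol use a broad test. Section 12.1.2 defines a related AE as "An AE which resulted from administration of any of the research procedures". Section 12.1.5 defines a related SAE as one at least possibly "related to the trial procedures". Section 10.8.6 names as reportable "A serious adverse event related to the trial procedures or intervention".

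Three places use a narrow one. Section 12.4, under which the site dentist grades causality, begins: "The assessment of relationship of adverse events to the intervention is a clinical decision". Section 12.5 says what counts as a related SAE, and its subject is "A serious adverse event whose causal relationship to the intervention is assessed by the dentist/delegated other". The minimum SAE information in 12.9.1 includes "One suspect intervention", and the matching entry is the CHOICE intervention, with no entry for a trial procedure.

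Sections 12.4 and 12.7 then limit site reporting to events that are serious and at least possibly related. Deaths are the exception: section 12.8 has them notified whatever their cause.

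**The concern.** Sections 12.1.5 and 12.5 define the same term, and the definitions disagree on what the event must be related to. The narrow version stands where causality is graded and where the SAE report is specified; the broad version stands in the definitions and in the list of reportable events.

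The difference matters most for controls. They do not receive DR-BNI. They do have the final dental assessment (10.7) and, if the family consents, saliva sampling at the randomisation visit and at 6 months (11.2). Under the narrow test no control-arm SAE can be related; under the broad test one can. Two sites that both follow the protocol could treat the same event differently, and the safety listing sent to the ethics committee and the IDSMC (12.12) would carry that difference.

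**Working it through.** The plan states no figure to reproduce. The check is a comparison of the text, followed by a count of contacts to show scope.

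**Step 1: one event under both tests.** Take a non-fatal SAE in a control child, caused by the 24-month examination or by saliva collection.

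| Section | Related to what? | Result |
|---|---|---|
| 12.1.2 (related AE) | research procedures | related |
| 12.1.5 (related SAE) | trial procedures | related |
| 10.8.6 (reportable events) | trial procedures or intervention | reportable |
| 12.4 (causality) | the intervention | not related |
| 12.5 (restated test) | the intervention | not related |
| 12.9.1 (minimum information) | the CHOICE intervention as suspect item | no entry fits |

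Under the first three rows the event goes to the LCTC within 24 hours. Under the last three, read literally, it does not qualify. The same holds for a procedure-related event in the intervention arm.

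**Step 2: is the grading checked later?** Only events graded serious and related leave the site (12.4, 12.7). The chief investigator then assesses expectedness for events already graded as related (12.12). The rule in 12.4 that a dentist's opinion is not lowered protects positive gradings only. The record reviews at 12 and 24 months (10.8) may bring an event to light, but it would still be graded under 12.4. A non-fatal event graded unrelated therefore has no routine central review.

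**Step 3: how much trial contact lies outside the narrow wording?**

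- DR-BNI sessions: 454, one per intervention participant (13.2.1).
- Final examinations: 908 × 0.80 = 726.4, about 726, using the 20% loss to follow-up in 13.2.1.
- Saliva collections: 400 children × 2 = 800 at most (11.2.4).
- Baseline examinations are left out. They precede randomisation (10.5.1), and active monitoring starts at randomisation (12.6).

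Total: 454 + 726 + 800 = 1,980. Intervention share: 454 / 1,980 = 22.9%.

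If the 400 samples at the randomisation visit are also left out, because they may be taken before allocation: 1,980 − 400 = 1,580, and 454 / 1,580 = 28.7%.

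So about 71% to 77% of these contacts are procedures that the narrow wording does not name. These are counts of contacts and say nothing about how often harm occurs.

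**The case against.** The strongest reply is that the broad definition governs. It stands in the terms and definitions, the 24-hour trigger in 12.9.1 uses the defined term, and 10.8.6 names trial procedures outright. Sections 12.7, 12.9 and 12.11 say only that the event must be related, without narrowing. A site that followed these would report the event. In 12.4 the references to time since the intervention are examples, and the grade definitions do not themselves limit what the cause may be. Section 12.5 mainly concerns expectedness, which the chief investigator assesses. The 12.9.1 list is a minimum, the form itself is not shown, and it asks for a description in which a procedure could be named.

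Most of this stands, and it limits the conclusion. It shows that some sites would report; it does not show that all would, because 12.4 and 12.5 still name the intervention alone.

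A reader might infer more than the documents support:

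- *Control-arm related SAEs are zero by definition, or all such harm is lost.* The broad passages give a route for reporting, and deaths are always notified.
- *A between-arm safety comparison is biased.* The Protocol plans no such comparison; 12.12.1 describes reporting rates and events by site.
- *Harm at baseline examinations is lost through this wording.* Those examinations fall outside the monitoring window however relatedness is defined.
- *Events at the final examination have no reporting route.* It is true that "The examiner/s will be independent to the general dental practices" and that the investigator's duty covers events "which the local research team becomes aware of are reported to LCTC". But 12.9 accepts that events may become known by any means, and the examiner's instructions may well lie outside the Protocol.

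**Conclusion.** The contradiction is real and bears on a reporting rule. A non-fatal SAE from the final examination or from saliva sampling is related under 10.8.6 and 12.1.5 and unrelated under a literal reading of 12.4 and 12.5. The supported consequence is that such events may be missed or classified inconsistently, most visibly in controls. It is not established that they will be.

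The practical size is small. The Protocol describes both procedures as non-invasive (10.7, 11.2.4) and rates the trial as low risk (14.4), so few events are likely. The 23% and 29% shares assume one DR-BNI session per intervention participant, 80% attendance at the final examination and full saliva collection at both visits. The point should still be corrected: the text gives two answers to one question, the safety listing inherits whichever answer each site chooses, and the correction is cheap.

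**What to change.** Amend 12.4 and 12.5 so that causality and the test for a related SAE are judged against the CHOICE intervention or any trial procedure, in line with 10.8.6, 12.1.2 and 12.1.5. In the 12.9.1 minimum information, let the suspect item name a trial procedure (final examination or saliva collection) as well as the CHOICE intervention, and match the SAE form field to it.

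The cost is a wording amendment, one form field and possibly a few extra reports over the trial. Sample size, outcomes and analysis are unaffected.

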### 12.5.1 Table 2: Expected Events

Event

Distress from parent/primary caregiver when discussing their child's oral health

## 12.6 **Time Period for Active Monitoring of Safety Events**

All related SAEs should be followed up until satisfactory resolution or until the dentist responsible for the care of the participant deems the event to be chronic or the patient to be stable. Active monitoring of safety events experienced by trial participants will be from the period of randomisation, until the patient has had their final 24 month examination.

## 12.7 Notes on Safety Event Recording

Due to the low-risk nature of the trial and the type of intervention, adverse events are not expected and do not need to be reported. Only adverse events that are deemed serious and possibly, probably and almost certainly related are to be reported to the LCTC. The assessment of seriousness of safety events should be performed by an appropriately delegated, medically qualified member of the site research team.

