### 5.3 Risk and Benefits

#### 5.3.1 Potential Risks

The intervention involves an interview using a personalised goal-centred approach to guide parents/primary caregivers on how to change habits that lead to tooth decay in favour of health promoting family routines. A trained dental nurse delivers the intervention face-to-face. It is possible that parents/primary caregivers may become upset when discussing their child's dental health. It is also possible that safeguarding issues could be disclosed during the intervention, and this will require the following of local guidance by the dental practices.

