At 12 months (+/- 3 months) post randomisation, the dental records will be reviewed to complete the following:

- Dental treatment and dental pain data recorded during the last 12 months
- Safety Data Assessment during the last 12 months

At 24 months (+/- 3 months) post randomisation, the dental records will be reviewed to complete the following:

- Dental treatment and dental pain data recorded during the last 12 months.
- Safety Data Assessment during the last 12 months.

Safety data can be collected as part of the study questionnaires.

A dental assessment will also be completed by a blinded assessor at 24 months (+/- 3 months).

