### 10.8.4 Process Evaluation

Mechanisms of impact will be investigated via qualitative interviews with up to 40 parents/primary caregivers 6-12 months after receiving the CHOICE intervention. An interview schedule will be developed to assess how the

intervention activities and participants' interactions trigger reported change in toothbrushing and sugar behaviours, maintenance of any behaviour change, automaticity, self-efficacy, intrinsic motivation, relief/regret and any unintended effects. Interviews will be conducted online/over the phone and audio-recorded for transcription and subsequent analysis.

Fidelity to the CHOICE intervention will be assessed from audio-recordings routinely undertaken as a part of the delivery of the intervention.

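### Parental distress, the only harm the protocol lists as expected, is not systematically counted in its usual non-serious form, and section 12.7 conflicts with sections 5.3.1, 12.5.1 and 12.3

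*Protocol*

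**What the plan says.** Section 5.3.1 of the protocol names two risks of the intervention. The first is emotional: "It is possible that parents/primary caregivers may become upset when discussing their child's dental health". The second is that a safeguarding matter may come to light. The expected-events table in 12.5.1 has a single row: "Distress from parent/primary caregiver when discussing their child's oral health".

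Section 12.7 then says that "adverse events are not expected and do not need to be reported", and sets the threshold: "Only adverse events that are deemed serious and possibly, probably and almost certainly related are to be reported to the LCTC". Section 12.4 gives the same rule: "only events that are classed as serious and possibly, probably or almost certainly related will be reported by participating site". Sections 10.8.6 and 12.9 agree with it.

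Section 12.3, by contrast, asks for a severity grade for every adverse event. The definition in 12.1.1 covers persons other than the trial subject, so a parent's reaction can be an adverse event.

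The schedule in 10.8 marks a safety assessment at the intervention visit and at 12 and 24 months. For the two later time points the text says that "the dental records will be reviewed to complete the following", with safety data among the items, and adds that study questionnaires can also carry safety data.

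**The concern.** The intervention works at the moment a parent learns that the child has decay. Section 5.1 says the parent is likely to be in a heightened emotional state and may anticipate regret. Distress is therefore the natural harm to watch, and the protocol says so in two places. Yet the reporting rule passes over that harm unless it is serious, and 12.7 says adverse events are not expected at all.

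The IDSMC is charged with interim safety monitoring (4.8.3) and receives an annual list of recorded safety events (12.12). That list would leave out the foreseen harm in its ordinary form. A final report of no related SAEs would be accurate but would not say how often parents were distressed. A decision to adopt the intervention in routine dental practice would reasonably want that figure.

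**Working it through.** **1. The passages side by side.**

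| Section | Position on parental distress |
|---|---|
| 5.3.1 | Foreseen as a possible risk |
| 12.5.1 | The only expected event |
| 12.1.1 | Can be an adverse event, since persons other than the subject are covered |
| 12.3 | To be graded for severity, like every adverse event |
| 12.7 | Adverse events are not expected and not reported |
| 10.8.6, 12.4, 12.7, 12.9 | Reported only if serious and related |

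Sections 5.3.1 and 12.5.1 cannot be squared with the word *expected* in 12.7. A grading of all adverse events (12.3) has little purpose if non-serious ones go nowhere. Section 12.5 also treats as unexpected any event that is more frequent or more severe than previously reported. For distress, the trial would hold no frequency of its own to apply that test.

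**2. Does another described route give a count?**

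- *Safety assessment at the intervention visit (10.8):* right time and right person, but only a related SAE is reportable (10.8.6).
- *Dental-record review at 12 and 24 months (10.8):* a child's dental record is a poor source for a parent's reaction to one conversation.
- *Study questionnaires (10.8):* may carry safety data, but the wording is permissive, the time points are 12 and 24 months, and the same threshold applies.
- *Visits, notes, direct report (12.9):* described only for events that are serious and related.
- *Audio recordings (9.2):* planned for all sessions, but checked for adherence to the intervention.
- *Feedback and Regret/Relief surveys (9.2, 10.8):* completed by the parent at the visit. Their contents are not shown and no distress count is described.
- *Discontinuation record (10.9, 10.9.1):* reasons for not completing the intervention are documented and withdrawals recorded. Distress is not among the examples, and distress in a completed session would not appear.
- *Process evaluation (10.8.4):* "qualitative interviews with up to 40 parents/primary caregivers 6-12 months after receiving the CHOICE intervention". At most 40/454 = 8.8% of the arm, and not a means of estimating a rate.

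**3. Size.** Section 13.2.1 requires 363 participants per group and allows for 20% loss: 363 / 0.80 = 453.75, rounded up to 454, and 2 × 454 = 908, as stated. The documents give no distress rate, so the rates below are assumptions, and every intervention parent is assumed to attend.

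| Assumed rate of non-serious distress | Parents affected (454 × rate) | Reportable under the rule |
|---|---|---|
| 1% | 4.5, about 5 | 0 |
| 5% | 22.7, about 23 | 0 |
| 10% | 45.4, about 45 | 0 |

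If distress were recorded, 23/454 = 5.1% would have a Wilson 95% interval of 3.4% to 7.5%, which is precise enough to be useful. By contrast, no related SAEs in 454 would give a one-sided 95% upper bound of 1 − 0.05^(1/454) = 0.66% for related SAEs. It would say nothing about non-serious distress.

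**The case against.** The strongest reply is that reporting only serious and related events is a reasoned choice. Sections 12.7 and 12.9 justify it by the nature of the trial and the intervention, and 14.4 classes the trial as low risk. The table in 12.5.1 is also not a list of events to collect. Under 12.5, expectedness decides whether a related SAE is reported as a RUSAE, so an expected event can fall below the reporting threshold without contradiction. Both points stand. They do not remove the wording conflict in 12.7, and they do not supply a count of the foreseen harm.

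A reader might infer that the trial will report no harm whatever happens, or that distress can never enter the data. The documents do not support that. Section 12.2 lets the investigator class an event as serious on medical significance, so serious related distress is reportable. All known deaths are notified (12.8). Intervention withdrawals and the reasons for non-completion are recorded (10.9, 10.9.1).

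A reader might also infer that distress is sought only in the child's dental record. That leaves out the questionnaires, the surveys, the session recordings, the interviews and the visit assessment itself. The rule governs what reaches the LCTC as a safety report. It does not forbid recording.

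Finally, the eCRF and survey contents are not shown. A distress item may already exist, although none is described.

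**Conclusion.** The point holds in a limited form. Parental distress, the one event the protocol lists as expected, is in its usual non-serious form neither systematically captured nor reported as safety data. Section 12.7 also conflicts with 5.3.1 and 12.5.1 and sits badly with 12.3. The text conflict needs no assumption.

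The number of events missed depends on a rate the documents do not give: about 5 to 45 parents for rates of 1% to 10%, with all 454 attending. The gap also assumes that the undisclosed eCRF and surveys hold no distress item. The primary outcome and its analysis are unaffected. This is a cheap improvement worth making.

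**What to change.** 1. At the safety assessment already scheduled at the intervention visit, record parental distress on the eCRF as yes or no, with the severity grade from 12.3.1.
2. Allow distress as a coded reason in the existing intervention-discontinuation record.
3. Report the counts to the IDSMC and in the final report.
4. Reword 12.7 to this effect: the expected event in 12.5.1 is recorded on the visit eCRF and summarised, but is not reported as an SAE unless serious and related; other non-serious adverse events are not collected. Align 10.8.6, 12.4 and 12.9. An exception added to the first sentence of 12.7 alone would contradict the sentence after it. Cite the table by section number, because 12.4 also contains a Table 2.
5. State in 12.3 which adverse events are to be graded.

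No separate safeguarding item is needed, since 10.8.2 already assigns those matters to local processes.

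The cost is about a minute of nurse time per session and one table. That table is descriptive and covers the intervention arm only, because control families have no session, so it gives a frequency and not a between-group comparison.
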